# **EXPERIMENTAL DESIGN SCHEMA**

\*\*\*If randomized to dietary intervention, participant will be asked to consume one 4 oz serving of Activia vanilla yogurt in the morning and one 4 oz serving of Activia vanilla yogurt in the evening for the duration of the study.

IRB Protocol No. 16088 Version Date: 06/12/2020

 ${\rm **Within~24~hours~of~onset~of~diarrhea~following~initiation~of~VEGF-TKI,~a~stool~sample~is~to~be~provided}\\$ 

\*If a participant ends VEGF-TKI before week 13, a final sample is to be provided, and the study logs to that time point are to be collected. Study participation will end at that time.

# **ABBREVIATIONS**

Abbreviation	Meaning
AE	Adverse event
CFR	Code of Federal Regulations
COH	City of Hope
CRA	Clinical research associate
CRF	Case report form
CTCAE	Common Terminology Criteria for Adverse Events
DSMC	Data Safety Monitoring Committee
FDA	Food and Drug Administration
GAD-7	Generalized Anxiety Disorder
GCP	Good clinical practice
ICF	Informed consent form
IRB	Institutional review board
MDSC	Myeloid-derived suppressor cells
NCI	National Cancer Institute
PBMC	Peripheral blood mononuclear cells
PHQ-9	Patient Health Questionnaire
PI	Principal investigator
PMT	Protocol monitoring team

IRB Protocol No. 16088

RPN Research patient number SAE Serious adverse event

IRB Protocol No. 16088 Version Date: 06/12/2020

#### 1.0 OBJECTIVES

#### Primary objective

 To determine if adding Activia™ yogurt (containing Bifidobacterium lactis DN-173 010) to the diet of patients with metastatic renal cell carcinoma (mRCC) increases the level of Bifidobacterium spp in stool.

# Secondary objectives

- To determine if Activia™ reduces the incidence of diarrhea for mRCC patients treated with vascular endothelial growth factor tyrosine kinase inhibitor (VEGF-TKI) therapy.
- To compare pre-treatment levels of circulating Treg cells and levels of peripheral STAT3 in
  patients with and without diarrhea with VEGF-TKI therapy, and correlate with Bifidobacterium,
  other bacteria, and Activia™.
- To determine if patients with the diarrhea in mRCC patients treated with VEGF-TKI therapy have a lower baseline level of *Bifidobacterium spp*.
- To assess the change in global stool microbiome profile of patients receiving therapy with VEGF-TKI therapy with or without Activia™
- To better assess the feasibility of stool collection and bacteriomic profiling.
- To explore association between psychosocial symptoms (anxiety and depression) and bacteriomic profile and gastrointestinal toxicity in mRCC patients receiving VEGF-TKI therapy.

#### 2.0 BACKGROUND AND RATIONALE

#### 2.1 Introduction and Rationale for Study

Recent Developments in mRCC: A Crowded Landscape

Over the past 6 years, a total of 6 targeted therapies have been approved for the treatment of mRCC. These agents can be divided into two principal categories: (1) inhibitors of the vascular endothelial growth factor receptor (VEGFR), and (2) inhibitors of the mammalian target of rapamycin (mTOR). The former category includes both VEGF-TKIs such as axitinib, sunitinib, pazopanib and sorafenib, as well as monoclonal antibodies such as bevacizumab that inhibit VEGFR through ligand binding. National Comprehensive Cancer Network (NCCN) guidelines recommend use of vascular endothelial growth factor directed therapies across different lines of mRCC treatment. For example sunitinib, pazopanib, axitinib, sorafenib and bevacizumab (the latter in combination with interferon- $\alpha$ , IFN- $\alpha$ ) is recommended for the first and subsequent lines of mRCC treatment and cabozantinib in the second and further lines of treatment... In contrast, the two currently approved mTOR inhibitors are generally implemented in more selected settings – for instance, everolimus is used after failure of VEGF-TKI therapy, while temsirolimus is used in patients with poor-risk disease or non-clear cell histology. All together, VEGF-TKIs are the most commonly utilized treatments in patients with mRCC in the United States.  $^3$ 

Limitations to Therapy: Managing Toxicity

The multitude of available agents for mRCC often makes it challenging for the oncologist and patient to select the appropriate therapeutic strategy. For instance, for the treatment-naïve patient with mRCC, how might the oncologist choose between the monoclonal antibody bevacizumab, and VEGF-TKIs? There are no head to head comparisons between the agents, and thusly, the oncologist is virtually forced to make cross-trials comparisons. Aside from considering the efficacy of these therapies across studies, the

IRB Protocol No. 16088 Version Date: 06/12/2020

oncologist may consider toxicity. Diarrhea appears to be particularly problematic with VEGF-TKI therapy, for example sunitinib nearly 50% of patients reporting some degree of diarrhea, usually first occurring within the first two cycles of therapy, and 10% of patients developing grade 3/4 toxicity (i.e., toxicities warranting dose modification or treatment discontinuation). In contrast, few patients experience severe diarrhea in association with bevacizumab therapy. The phenomenon of diarrhea appears to be quite consistent across VEGF-TKIs, as seen in Table 1. Notably, even VEGF-TKIs used in the second line setting, such as axitinib, yield similar rates of diarrhea. The frequency of diarrhea encountered with these agents is quite startling.

Table 1. Frequency of diarrhea reported in pivotal phase III trials assessing VEGF-TKIs for mRCC.1,2,3

Agent	N	Grade 1 or 2	Grade 3 or 4	Overall
Sorafenib	451	41%	2%	43%
Sunitinib	375	52%	9%	61%
Pazopanib	290	48%	4%	52%
Cumulative	1116	47%	5%	51%

# Bacteriomic Profiling: A Laboratory-Based Biomarker of VEGF-TKI Induced Diarrhea?

Recent technological advances now allow for complete bacteriomic profiling of intestinal flora using 16S rRNA sequencing.8 Although such techniques have not been utilized specifically in the context of cancer therapeutics, there is existing data using fecal DNA sequencing that suggests the composition of intestinal flora can influence the development of diarrhea with specific cytotoxics. For instance, in the context of irinotecan therapy, Stringer et al have performed an elegant series of experiments in preclinical models suggesting that β-glucoronidase-producing Escherichia coli (which metabolize irinotecan) may increase during the course of irinotecan therapy.8 The increase in E. coli in turn exacerbates observed gastrointestinal toxicity.

There is rationale for VEGF-TKI therapy altering the intestinal flora. Our group has previously published data suggesting an immune-mediated effect of sunitinib, decreasing T-regulatory (Treg) cell populations via STAT3.9 Separately, it is documented that Tregs may play a role in gut homeostasis, promoting tolerance of various luminal bacteria.  Taken together, sunitinib and other VEGF-TKI agents in the same therapeutic class may promote an autoimmune response that shifts the equilibrium of intestinal flora composition.

[figure not shown]
#### Protective Effect of Probiotics

In contrast, "gastrointestinal protective" bacterial, such as Bifidobacterium spp., decreased during the course of treatment. Notably, probiotic formulations including Bifidobacterium spp. have been noted to improve acute diarrhea in a multitude of settings. 11,12 A recently completed randomized, phase II study comparing one such probiotic to placebo in patients receiving radiotherapy for cervical cancer showed an improvement in the incidence of diarrhea with probiotic treatment.

IRB Protocol No. 16088 Version Date: 06/12/2020

# COH IRB 12096: A Pilot Study

The current team of investigators embarked on a project sponsored by the COH Cancer Center Core Grant. We collected random stool samples from a cohort of 23 patients with mRCC while receiving VEGF-directed therapies. Ultimately, 20 patients provided satisfactory samples for evaluation. Amongst these patients, the majority were treated with sunitinib or pazopanib. 16S rRNA profiling using the methods described herein was used to characterize the stool bacterial flora of these patients. Patients receiving VEGF-TKIs with mRCC appeared to have less relative abundance of Bifidobacterium spp as compared to previous reports based on healthy subjects. Patients also had higher levels of Bacteroides spp and lower levels of Prevotella spp were found in patients with diarrhea.

We interpret the results of COH IRB 12096 cautiously, as there are several caveats to this work:

- 1. The sample size is small,
- 2. There was heterogeneity of treatments rendered
- 3. Stool collections were done at random time points
- 4. There was no control of dietary factors

Despite the aforementioned limitations, COH IRB 12096 established the feasibility of stool collections and subsequent bacteriomic analysis and suggested the possibility that the propensity for the diarrhea observed could be due to the low abundance of Bifidobacterium spp observed in this patient population and that supplementing with Bifidobacterium would change the flora and also change the relative abundance of Bacteroides. An SOP for stool collection and analysis was developed that will be implemented in the current study.

### Psychosocial aspects

The management of psychosocial symptoms (anxiety and depression) has gained attention in cancer care. In this scenario, there is evidence showing the association between psychosocial and physical symptoms.

Gastrointestinal symptoms, particularly diarrhea, is one of the common side effects among cancer patients who are receiving sunitinib therapy, and it is known that mood could be influenced by gastrointenstinal manifestations and biological mechanisms (as abnormalities in the gut-brain axis, shared genetic factors, inflammation) in gastrointestinal chronic inflammatory diseases; however little is known about the relationship between psychosocial symptoms, bacteriomic profile and gastrointestinal toxicity in mRCC patients. Therefore, future studies should be conducted in order to understand this association.

To date, there is relatively limited data to characterize the symptoms of anxiety and depression in patients with renal cell carcinoma. There is no specific measure for assessing these symptoms in patients with mRCC, except for a recent guideline for screening, and assessment of anxiety and depressive symptoms in adults with cancer. Generalized Anxiety Disorder (GAD)-7 is recommended as a good measure to assess significant symptoms of anxiety, and the Patient Health Questionnaire for Depression (PHQ)-9 of depression. Both measures are based on the Diagnostic and Statistical Manual of Mental Disorders (DSM).

IRB Protocol No. 16088 Version Date: 06/12/2020

The GAD-7 is a one-dimensional self-administered scale designed to assess the presence of the symptoms of anxiety. Score is calculated by simple addition of the answers to each item. Scores for all 7 items range from 0 (not at all) and 3 (nearly every day). Therefore, the total scores ranges from 0 and 21, and may be categorized into four severity groups: minimal (0-4), mild (5-9), moderate (10-14) and serious (14-20).Questionnaire administration time is 5 minutes.

The PHQ-9 focuses on the nine signs and symptoms of depression from the DSM, and has a dual-purpose, to establish a provisional disorder diagnosis and to provide a symptom severity score. High scores indicate increasing severity of depression. For a diagnosis of depression, five or more items must be scored as present more than half of the days or nearly every day. A PHQ-9 score of 5-9 indicates minimal depressive symptoms, a score of 10-14 is minor depression or major depression that is mild, a score of 15-19 is major depression, moderately severe, and a score > 20 indicates major depression, sever. Questionnaire administration time is 5 minutes.

Patients will be assessed for anxiety and depression at 2 distinct time-points: at baseline (before starting sunitinib - T1) and at week 13 (T2) to match the proposed assessments of stools and gastrointestinal toxicity.

# 2.2 Overview and rationale of study design

Diarrhea is a significant toxicity experienced by roughly 50% of patients treated with VEGF-TKIs. Identifying a pre-treatment biomarker associated with treatment-related diarrhea may lead to the development of a pre-treatment conditioning regimen. Data from our pilot study in metastatic renal cell carcinoma (mRCC) patients undergoing VEGF-TKI therapy demonstrated a notably low abundance of Bifidobacterium spp. The primary objective of this study will be to ascertain whether or not the simple addition of Activia™ yogurt (containing Bifidobacterium lactis DN-173 010) will reduce this dysbiosis. Changing the abundance of this species, and indirectly other species in the complex microbiota population prior to initiating therapy may decrease in VEGF-TKI related diarrhea.

Twenty patients with mRCC will be recruited prior to initiating standard of care therapy with VEGF-TKIs, and will be followed for three months of therapy for specimen and data collection. Patients will be treated according to NCCN guideline recommendations for each VEGF-TKI agent. An intervention will be performed. Specifically, patients will be randomized to either a probiotic-supplemented group (Activia™) or a probiotic-restricted group using a permuted block design to ensure the 20 patients were assigned to the two groups with 1:1 ratio. Patients in the probiotic-supplemented group will be asked to consume one 4 oz serving of Activia vanilla yogurt in the evening daily for the 3 month study period and patients in the probiotic-restricted group will be asked to avoid any intake of yogurt or yogurt-containing foods for the evaluation period of the study.

Several stool collections will be performed. Stool samples will be collected prior to initiating VEGF-TKI treatment, one week after initiating therapy, two weeks after initiating therapy, three weeks after initiating therapy (i.e. after the first week off of therapy), three months (13 weeks) into VEGF-TKI therapy, and at the onset of diarrhea. A stool specimen at the onset of diarrhea would reflect changes in the bacteriome that could potentially drive onset of this symptom. Compliance with stool submission has not been an issue in our pilot study (IRB 12096). All stool samples will be collected by the participant at home and sent via overnight shipping to the laboratory at City of Hope. Participants will receive training on the sample collection process. Participants will also be asked to complete a diet log and stool frequency log that uses the CTCAE v4.0 definitions of diarrhea:

IRB Protocol No. 16088 Version Date: 06/12/2020

- Grade 1: Increase of <4 stools per day over baseline; mild increase in ostomy output compared to baseline
- Grade 2: Increase of 4 6 stools per day over baseline; moderate increase in ostomy output compared to baseline
- Grade 3: Increase of >=7 stools per day over baseline; incontinence; hospitalization indicated; severe increase in ostomy output compared to baseline; limiting self care ADL
- Grade 4: Life-threatening consequences; urgent intervention indicated
- Grade 5: Death

For purposes of the current study, we are interested in characterizing the incurrence of all grade diarrhea (e.g., grade 1-5 toxicity); however, the grade of diarrhea incurred will be specified.

From the serial stool samples, *Bifidobacterium spp*. levels and stool bacteriomic profile over time will be assessed and associations will be examined between patients who experience diarrhea and those who do not.

To explore potential confounding factors or associations of interest between the bacteriomic profile and the presence of diarrhea, data collection will include: intake of yogurt, general description of daily diet, prior anti-cancer therapies, concomitant medications during the study period, and response to VEGF-TKIs. These data will be collected from the participant's medical record or from the participant's daily log.

As differences in intestinal flora may be immune-mediated, pre-treatment levels of circulating T-regulatory cells, myeloid derived suppressor cells and levels of peripheral STAT3 will be compared in patients with and without treatment-related diarrhea. For these analyses, participants will provide a 10-ml blood sample at the time of three stool specimen collections (prior to initiating VEGF-TKIs, two weeks after initiating therapy, and three months into therapy).

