# Secondary Objectives:

 To determine if the Activia™ reduces the incidence of diarrhea for mRCC patients treated with VEGF-TKIs.

We will compare the rate of all grade diarrhea in patients who receive the dietary supplement and those who do note. The rate of grade 3/4 diarrhea will also be compared between the two groups. A Fisher's exact test with a 0.050 one-sided significance level will have 80% power to detect the difference between the Activia™ group proportion with diarrhea, ②₁, of 0.200 and a non-Activia™ proportion, ②₂, of 0.800 when the sample size in each group is 10.

2) To compare pre-treatment levels of circulating Treg cells and levels of peripheral STAT3 in patients with and without diarrhea with sunitinib therapy, and correlate with Bifidobacterium, other bacteria, and Activia™:

Treg quantity is a secondary measurement and an analysis will be carried out to evaluate whether Tregs expression differs in patients who develop diarrhea with VEGF-TKI therapy as compared to patients who do not. The distribution of the Treg quantity will be examined and log transformation may be applied if the distribution is skewed. Parametric or nonparametric test will be used to compare Tregs between the the diarrhea and non-diarrhea groups, and between the Activia™ and non-Activia™ groups.

3) To determine if patients with the diarrhea in mRCC patients treated with VEGF-TKI therapy have a lower baseline level of *Bifidobacterium spp*.

IRB Protocol No. 16088 Version Date: 06/12/2020

Once diarrhea has occurred, the Bifidobacterium spp may be reduced. We will compare the abundance of Bifidobacterium spp. Between diarrhea and non-diarrhea patients and the change in Bifidobacteria in patients who subsequently get diarrhea.

4) To explore association between psychosocial symptoms (anxiety and depression) and bacteriomic profile and gastrointestinal toxicity in mRCC patients treated with VEGF-TKIs. We will dichotomize the population based on low or high depression (and subsequently low and high anxiety). Using descriptive statistics, we will then assess differences in response rates, gastrointesntinal toxicity, microbial diversity and immune biomarkers.

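### The marker-by-diarrhea comparisons take no account of randomised arm: pre-treatment markers are only diluted, but post-baseline Bifidobacterium comparisons would be confounded

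*Combined protocol and SAP*

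**What the plan says.** Section 2.2 gives the aim: "Identifying a pre-treatment biomarker associated with treatment-related diarrhea may lead to the development of a pre-treatment conditioning regimen". It then says that pre-treatment Treg cells, "myeloid derived suppressor cells and levels of peripheral STAT3 will be compared in patients with and without treatment-related diarrhea".

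Section 8.1, secondary item 2, plans to "evaluate whether Tregs expression differs in patients who develop diarrhea with VEGF-TKI therapy as compared to patients who do not", by a parametric or nonparametric test, with a log transformation if the data are skewed. It adds a second, separate test of Treg between the arms. MDSC appears in section 2.2 but not in this item.

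Item 3 is titled as a question about baseline Bifidobacterium. Its text compares abundance by diarrhea status without fixing a time point, and also looks at change in patients who go on to have diarrhea.

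Neither item names an arm covariate, a stratified test or an analysis by arm. The secondary objective speaks of correlating the markers with Activia, and section 2.2 collects yogurt intake to explore confounding. Neither defines an adjusted analysis.

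Arm-specific diarrhea rates appear only in item 1, where the "exact test with a 0.050 one-sided significance level will have 80% power" for an Activia proportion "of 0.200 and a non-Activia™ proportion" "of 0.800 when the sample size in each group is 10". Allocation is made "using a permuted block design to ensure the 20 patients were assigned to the two groups with 1:1 ratio".

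**The concern.** The comparison groups are formed by an outcome that the trial's own intervention is meant to change. If yogurt prevents diarrhea, a susceptible patient in the Activia arm is counted as diarrhea-free beside a resistant control. The two groups then differ less on the marker than they would within either arm. A negative marker result might partly reflect the intervention, and finding a pre-treatment marker is part of the stated rationale.

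Item 3 carries a second and more serious risk. Activia is intended to raise Bifidobacterium and to lower diarrhea. Any comparison of post-baseline levels or of change by diarrhea status that ignores arm can therefore show an association that is only the effect of allocation on both.

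**Working it through.** **Inputs from the documents.** 10 patients per arm; diarrhea 0.20 (Activia) v 0.80 (control) as the powering alternative in 8.1 item 1; background diarrhea about 50% (section 2.2; Table 1 gives 43% to 61%, cumulative 51%).

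**Assumptions, not in the documents.** Marker effect of 0.5 to 2 in log odds ratio per SD; two-sided 0.05, since no sidedness is given for the marker tests; Activia-arm rates of 0.20, 0.30 or 0.50 when the control rate is 0.50.

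**1. The plan's own figure.** Exact enumeration of the one-sided 0.05 Fisher test, 10 v 10, at 0.20 v 0.80 gives 80.5%. The stated 80% is reproduced.

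**2. Who is in each group at 0.80/0.20.** With diarrhea: 10 × 0.80 = 8 controls and 10 × 0.20 = 2 Activia. Without: 2 controls and 8 Activia.

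**3. Large-sample efficiency of the pooled test.** This is the mean of p(1−p) over arms, divided by p̄(1−p̄).
- 0.80/0.20: 0.16/0.25 = 0.64
- 0.50/0.20: [(0.25 + 0.16)/2]/(0.35 × 0.65) = 0.205/0.2275 = 0.90
- 0.50/0.30: [(0.25 + 0.21)/2]/(0.40 × 0.60) = 0.23/0.24 = 0.96
- 0.50/0.50: 0.25/0.25 = 1

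**4. Power with 10 per arm.** Simulation, 40,000 trials per cell. The marker is standard normal and independent of arm. Diarrhea is logistic in arm and marker, with intercepts set to give the stated arm rates. Entries are power (%) of the pooled t-test v the linear model with arm, two-sided 0.05.

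| Control/Activia rate | log OR 0.5 | 1.0 | 1.5 | 2.0 |
|---|---|---|---|---|
| 0.80/0.20 | 9.5 v 12.0 | 21.8 v 31.3 | 35.4 v 51.9 | 46.4 v 67.1 |
| 0.50/0.20 | 14.0 v 14.4 | 35.8 v 37.4 | 58.3 v 61.3 | 74.5 v 77.7 |
| 0.50/0.30 | 15.6 v 15.5 | 42.3 v 41.8 | 66.7 v 66.5 | 82.9 v 82.6 |
| 0.50/0.50 | 17.0 v 16.3 | 46.8 v 44.6 | 73.5 v 70.7 | 88.6 v 86.2 |

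At 0.80/0.20 the losses from pooling, before rounding, are 2.4, 9.5, 16.5 and 20.7 points. At one-sided 0.05 they are 3.7, 11.0, 16.1 and 17.6. With no marker effect both tests reject about 5% of the time. For rank tests (Mann-Whitney v van Elteren, two-sided), the gain from stratifying at 0.80/0.20 is 1.8 to 19.2 points over the same effects, and the cost at 0.50/0.50 is 1.3 to 6.0 points.

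**5. Post-baseline values.** Assume an arm shift in Bifidobacterium of 1.16 SD, which gives a one-sided 0.05 t-test 80% power with 10 per arm, and no association with diarrhea given arm. At nominal two-sided 0.05 the pooled test then rejects in 28% of trials at 0.80/0.20 and in 10% at 0.50/0.20. The arm-adjusted test rejects in about 5% of trials in both cases.

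**6. Thin cells.** At 0.80/0.20 a given arm has no within-arm contrast with probability 0.8¹⁰ + 0.2¹⁰ = 0.107. It has one patient or fewer in its smaller outcome group with probability 0.376, so at least one arm does with probability 1 − (1 − 0.376)² = 0.61.

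**The case against.** The strongest case against is that 0.80 v 0.20 is not a forecast. It is the difference that a Fisher test with 10 per arm can detect, and its control rate is far above the plan's own background of about 50%. This stands. Near that background the gain from adjustment is small, and its sign depends on whether yogurt works.

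The size of the loss also depends on a marker effect that the documents do not give, and a weak marker loses little even at 0.80/0.20. This stands too.

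A reader might infer that the baseline contrast is confounded, because most patients with diarrhea would be controls. The documents do not support that. Under randomisation a marker measured before any yogurt is independent of arm, and the type I error stays at 5%. The premise does need securing. The documents do not say when randomisation takes place relative to the baseline samples. The activity table in section 4.1 marks the dietary intervention in the pre-treatment column, while its footnote n starts it at week 2.

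A reader might also infer that pooling hides the marker. It weakens the contrast without removing it: at an odds ratio of 4.5 per SD, the marker difference falls from 1.06 SD at 0.50/0.50 to 0.72 SD at 0.80/0.20. With 20 patients a null result is uninformative for most of these effects under either analysis.

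Finally, a control-arm estimate would rest on about 2 diarrhea-free patients at 0.80/0.20. If the marker acts alike in both arms, it has less power than pooling (26% v 35% at log OR 1.5). That rules it out as the main test. It can still serve as description.

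**Conclusion.** The concern holds in a limited form. The plan is silent on arm in comparisons whose grouping variable the intervention is meant to alter.

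For truly pre-yogurt markers the consequence is lost efficiency only. It is material if Activia works about as strongly as the powering alternative and the marker is moderate to strong. It is about 2 points for a weak marker, and small, nil or slightly reversed when control diarrhea is near 50%. The 64% efficiency figure needs no assumed marker effect, but it does need the 0.80/0.20 rates, which the plan does not predict.

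For post-baseline or change comparisons of Bifidobacterium in item 3 the consequence is confounding, with a false-positive rate of 10% to 28% under the assumed arm shift.

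These are secondary analyses and the primary comparison is unaffected. Adding arm is still worthwhile, because the possible recovery is larger than the possible cost.

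**What to change.** In section 8.1, items 2 and 3:

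- Make the main marker-by-diarrhea comparison a linear model of the marker, log-transformed where skewed, on diarrhea status and randomised arm. Name the van Elteren (stratified Wilcoxon) test as the nonparametric alternative.
- Report the control-arm difference with its confidence interval, labelled as descriptive.
- Use the same arm term in any post-baseline or change comparison of Bifidobacterium, and state the time point of each comparison.
- State when randomisation takes place relative to the baseline samples, define baseline as sampled before the first yogurt, and reconcile the section 4.1 table with its footnote n on when the dietary intervention starts.
- List MDSC in item 2 if it is to be analysed as section 2.2 says.

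The cost is wording only, since arm is already recorded. The statistical price, if yogurt has no effect on diarrhea, is about 1 to 3 points of power for the linear model and up to about 6 for the stratified rank test.
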